9.3.3 Secondary Endpoint Analysis

The fitting data provided by the fitting software will be exported and sent to the sponsor without any personal labeling. A secondary analysis is planned on the fitting data in an exploratory framework. The purpose of this analysis is to train and evaluate a predictive algorithm (Kollmeier et al., 2016). The algorithm predicts an SRT based on the audiogram and the hearing aid fitting and will be compared to the one measured in the secondary objective: SRT for hearing aid benefit.

This secondary analysis doesn't influence the objective and will not be part of the clinical investigation report. A separate report will be provided about the predictive algorithm to show that the data were used as described in this clinical investigation plan.

9.3.4 Interim Analysis

The clinical investigation has three independent parts focusing on beamformer performances, Speech Enhancer, and Hearing Aid Benefit. A separate statistical analysis for each part will be

provided as soon as all the recruited participants have completed the 2nd visit (for the beamformer and hearing aid benefit parts) and the 4th visit (for the remaining part).

9.3.5 Safety Analysis

The adverse event risks of taking part in the study have been assessed to be low. Numbers of adverse events (AE), serious adverse events (SAE) and device deficiencies (DD) will be cross-tabulated and categorized by severity. No formal statistical analysis will be conducted, but AEs SAEs, and DD will be closely monitored throughout the process. Serious Adverse Events (SAEs) will be recorded, and the site will notify the trial monitor of any SAE, who will then notify the project sponsor within one working day.

9.3.6 Deviation(s) from the original statistical plan

The description of all deviations from the original statistical plan will be provided in the Clinical Investigation Report including proper justification.

9.3.7 Handling of missing data and drop-outs

Unless specified otherwise in each objective, no statistical techniques will be used to impute missing data. If a subject's data are missing for any reason, that subject will not be included in that portion of the analysis. The number of subjects included in each analysis will be reported so that the potential impact of missing data can be assessed.

10 Investigation Duration and Investigation Schedule

Total expected duration of the clinical investigation is 5 months.

Expected duration of each participant's participation is:

Screening visit: 60 minutes

Visit 1: max 120 minutes

Visit 2: max 120 minutes

Visit 3: max 120 minutes

Visit 4: max 120 minutes

11 Data Handling and Management

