The measure of the speech reception threshold (SRT) is a procedure to evaluate the speech intelligibility in different listening conditions. The SRT in noise is defined as the signal-to-noise ratio (SNR) needed to understand 50% of the presented sentences. The SRT can be obtained with an adaptive procedure to overcome floor and ceiling effects, where the SNR is adapted based on the intelligibility score of the previous sentence. The adaptive procedure is defined so that the test conditions lead to a SNR with 50 % speech intelligibility: the SNR for the next sentence is decreased (more difficult situation) when the presented sentence is correctly understood or the SNR is increased (easier situation) when the presented sentence is not correctly understood. For the adaptive procedure, the noise is presented at fixed 65 dB level and the speech level is adapted according the reference procedure. The Oldenburg Sentence Test (OLSA) is a standard speech intelligibility test in German (Wagener et al., 1999 a-b-c) recommended for the evaluation of hearing aid performances (Kollmeier et al., 2011). The OLSA test uses nonsense sentences with equivalent difficulty. The OLSA test was already used for previous evaluations of the R-BF with the talker located in the front (Neher et al., 2017). The OLSA will be repeated in 8 times for the primary objective: 2 test conditions (R-BF and I-BF) by two talker locations (speech from the side and speech from the back) by two test sessions (test at visit 1 and retest at visit 2); in 3 test conditions for the secondary objective with the speaker from the front: unaided, aided with Fixed Directional and aided with Stereo Zoom. The SRT (in dB SNR) is provided for each OLSA measure.

2) ACALES: Listening effort

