random slope. The fixed effects are sum coded to get estimate of test setup and device that are easily interpreted.

The estimated effects are:

- test setup effect -0.6 dB SNR in average with a standard error of 0.2 dB SNR,
- device effect -3.0 dB SNR in average with a standard error of 0.4 dB SNR,
- interaction setup by device -1.6 dB SNR in average with a standard error of 0.4 dB SNR.

The effects of talker location and directional microphone are in line with data from Giuliani & Brayda (2019) who report SRTs measured with a single talker from different azimuth (from the back and the side) and different beamformers. While the test was performed with a different population (normal hearing listeners), different beamformers (virtual reality glasses) and test material (SRT in Italian with the Bocca test), the effects are similar with the reference data i.e., a decrease of 0.5 dB SNR when the talker is in the back instead of the side, a decrease of 4.5 dB SNR for the wider beamformer compared to narrower one, and a negative interaction of 0.5 dB SNR.

Results from both studies are consistent in direction even if there are some differences in their amplitudes. These observations are providing enough confidence for the simulation and we can therefore estimate the power based on the reference data for different sample sizes.

d. Simulation

We will make use of the mixed power function from the mixedpower package (Kumle et al., 2018, version 0.1.0) with varying sample size, since we want to compute the power for different sample sizes. The following simulation is based on 1000 runs with a varying sample size from 16 to 28. This range of sample sizes is usually reported in published articles about the effect of directional microphones and is also acceptable from a time and resources perspective.

Simulation is repeated two times. First on original data set where simulations rely on the same effect size provided by the reference model, which might be overpowered for the device effect. This increases the risk to perform analysis with inflated effect sizes and limit the chance of reproducing the results. The alternative is to specify the smallest effect size of interest (SESOI).

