9.3.2 Primary Endpoint Analysis

All the statistical tests will be performed at two-sided $\alpha=0.05$ if not specified differently. All reported p-values greater than or equal to 0.001 will be rounded to three decimal places and p-values less than 0.001 will be displayed as "<0.001". The analysis will be run using the statistical software R, version 4.1.1 (2021) (R Core Team 2021). The statistical analysis report will be written in a Rmarkdown format and exported into an HTML document.

a) Demographic Data

The following demographic and baseline characteristics will be tabulated overall for PP population: Age (years), 4-frequency Pure Tone Average (in dB HL), and case history i.e., hearing loss onset, otalgia, otorrhea, otitis, tinnitus.

For continuous variables (e.g., age) descriptive statistics will be presented (mean, interquartile range, and number of participants with data). For categorical variables frequencies, percentages and number of participants with data will be presented. The denominator for the percentages will be the number of patients with non-missing data.

b) Primary outcome: SRT for directional benefit

The SRT is a continuous variable expressed as the signal-to-noise ratio (in dB) necessary to achieve 50% intelligibility of the presented sentences. The SRT is measured in a 2 by 2 factorial design: talker factor (from the side or from the back) and beamformer (R-BF or I-BF). These SRTs will be analyzed with a linear mixed effect model with sequence (test-retest), talker location, beamformer, and interaction between location and beamformer as fixed effects. Participants will be treated as random factor with beamformer as random slope. The fixed effects are sum coded to get estimate of talker position and beamformer that are easily interpreted. The distribution of residuals will be visually checked to be independent and identically distributed. A likelihood ratio test will be made to obtain a p-value for each fixed effect.

c) Secondary outcome: listening effort for directional benefit

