The listening effort is measured in dB SNR for three effort rating: no effort (1), moderate effort (7), and extreme effort (13). Lower SNRs indicate that the participant can tolerate more noise for the same subjective rating and stand therefore for better results. The ACALES results are measured with 2 talker locations, 2 beamformer settings, and twice (test-retest). Listening effort will be analyzed with a linear mixed effect model with sequence (test-retest), talker location, beamformer, and rated effort as fixed effects. Participants will be treated as random factor with beamformer as random

slope. The fixed effects are sum coded to get estimate of talker position and beamformer that are easily interpreted. The distribution of residuals will be visually checked to be independent and identically distributed. A likelihood ratio test will be made to obtain a p-value for each fixed effect.

d) Secondary outcome: listening effort for SE benefit

The ACALES will be repeated for 3 distances and 2 conditions (SE Off vs On). The outcome is a rating on a 13 points scale, as the difficulty is fixed by the distance now. The outcome is discrete and bounded at both ends so that a non-parametric test should be applied. Wilcoxon signed rank test will be made for each distance and Bonferroni correction for multiple comparison will be made for the three distances.

e) Secondary outcome: speech test for SE benefit

Word recognition is measured in percent for 2 conditions (SE Off vs On) and in two independent setups: 4 m distance and talker in adjacent room. Percent scores will be converted to arcsin units (Sherbecoe & Studebaker, 2004) for variance normalization. A paired t-test will be made for each condition, as the test setups address different and unrelated listening conditions.

f) Secondary outcome: subjective assessment questionnaire.

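### As most naturally read, section 9.3.7 drops a whole participant from the primary SRT mixed model when any of the 8 SRTs is missing, although that model can use incomplete participants without imputation

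*Combined protocol and SAP*

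**What the plan says.** Section 9.3.7 rules out imputation unless an objective says otherwise. It then states that if a subject's "data are missing for any reason, that subject will not be included in that portion of the analysis". The next sentence adds: "The number of subjects included in each analysis will be reported so that the potential impact of missing data can be assessed".

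Section 6, item 1, sets the number of primary measurements: "The OLSA will be repeated in 8 times for the primary objective: 2 test conditions (R-BF and I-BF) by two talker locations", each at visit 1 and again at visit 2. Each visit therefore holds one full 2 by 2.

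Section 9.3.2 b) gives the primary model: "These SRTs will be analyzed with a linear mixed effect model with sequence (test-retest), talker location, beamformer", plus the location-by-beamformer interaction, a random participant effect and a random beamformer slope. It contains no missing-data rule of its own. Section 9.3.2 c) uses the same kind of model for ACALES: "Listening effort will be analyzed with a linear mixed effect model with sequence (test-retest), talker location, beamformer, and rated effort as fixed effects".

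Section 9.3.1 removes participants who withdraw only if they do not want their collected data used. Section 9.1 e) plans 20 participants for 80% power at 1.0 dB and adds 10% for drop-out, giving 22.

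**The concern.** The unit that 9.3.7 excludes is the subject, not the missing measurement. The following sentence counts subjects per analysis, so a portion most naturally means one outcome analysis. Read that way, a participant with a complete 2 by 2 at visit 1 who misses visit 2 contributes nothing to the primary test. Nor does a participant with 7 of the 8 SRTs.

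The chosen model does not need this. A likelihood-based mixed model takes whatever measurements a participant has, and keeping them is not imputation. Subject-level deletion suits the paired tests in 9.3.2 d) and e), where half a pair carries no information, but not the repeated-measures models.

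ACALES in 9.3.2 c) is exposed in the same way, with 8 runs x 3 effort levels = 24 values per participant. The three levels come from one fitted curve, so the run is the realistic unit of loss.

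At stake are the precision of the primary beamformer effect and a primary dataset that the plan does not fix in advance.

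**Working it through.** **The plan's own figures.** 20 x 1.10 = 22, as stated. The 80% came from simulation on individual data that are not in the document, so it cannot be reproduced exactly. As a rough check, power = Φ(1.0/SE − 1.96). The reported device SE of 0.40 gives Φ(0.54) = 70.5%; its lower rounding limit, 0.35, gives Φ(0.897) = 81.5%. Because the level is uncertain, the standard-error results come first (they need no power calibration) and power is shown under several calibrations.

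**Variance ratio.** Section 9.1 c) reports three effects with their standard errors, for 20 users. Assume a two-beamformer 2 by 2 with effects expressed as differences. Write s² for residual variance and t² for random-slope variance.
- Setup, reported as "test setup effect -0.6 dB SNR in average with a standard error of 0.2 dB SNR": here 0.2² = s²/20, so s² = 0.8.
- Interaction, reported as "interaction setup by device -1.6 dB SNR in average with a standard error of 0.4 dB SNR": here 0.4² = 4s²/20, so s² = 0.8 again.
- Device, reported as "device effect -3.0 dB SNR in average with a standard error of 0.4 dB SNR": here 0.4² = (t² + s²)/20, so t² + s² = 3.2 and t² = 2.4.
- Ratio r = t²/s² = 3. Rounding of the SEs (0.35 to 0.45 for interaction and device) gives s² = 0.6125 to 1.0125 and t² + s² = 2.45 to 4.05, so r = 1.42 to 5.61.

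**Information kept by an incomplete participant.** The beamformer contrast has variance t² + s²/2 from 8 SRTs and t² + s² from visit 1 alone. The visit-1-only fraction is therefore f = (r + 0.5)/(r + 1): 0.875 at r = 3, 0.793 at 1.42, 0.924 at 5.61, 0.5 at r = 0, and 1 with no residual variance. For one SRT missing of 8, generalised least squares in the planned model gives about 0.976 at r = 3 (0.958 at 1.42, 0.986 at 5.61). Deletion gives both kinds of participant zero weight.

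**Standard error, deleted relative to kept.** With k incomplete participants of 22, the ratio is sqrt((22 − k + k·f)/(22 − k)).

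| Case | k = 2 | k = 4 |
|---|---|---|
| Visit 1 only, r = 3 | sqrt(21.75/20) = 1.043 | sqrt(21.5/18) = 1.093 |
| Visit 1 only, r = 1.42 to 5.61 | 1.039 to 1.045 | 1.085 to 1.098 |
| Visit 1 only, any r | 1.025 to 1.049 | 1.054 to 1.106 |
| One SRT missing, r = 3 | 1.048 | 1.103 |

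**Power for 1 dB (visit 1 only, r = 3).** Power = Φ(sqrt(N/V) − 1.96), with N = 22 − k if deleted and N = 22 − k + k·f if kept.

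| Calibration | V | k = 2, deleted vs kept | k = 4, deleted vs kept |
|---|---|---|---|
| A: 80% at n = 20 refers to 8 SRTs | 20/(1.960 + 0.842)² = 2.548 | 80.0% vs 83.2% | 75.7% vs 82.8% |
| B: 80% at n = 20 refers to one 2 by 2 | 2.548 x 0.875 = 2.230 | 85.0% vs 87.8% | 81.1% vs 87.4% |
| C: SE 0.4 at n = 20 from one 2 by 2 | 3.2 x 0.875 = 2.8 | 76.2% vs 79.6% | 71.8% vs 79.1% |
| SE 0.4 taken for the 8-SRT design | 3.2 | 70.5% vs 74.1% | 66.0% vs 73.6% |

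Over any variance ratio, the difference for k = 4 is 4.3 to 7.9 points under A and 1.3 to 7.9 under B. The upper end needs zero residual variance.

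**Isolated losses (illustration only).** If each SRT were lost independently with probability 1%, 2% or 5%, the expected number with all 8 is 22 x (1 − p)^8 = 20.3, 18.7 or 14.6. These rates are assumptions.

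**The case against.** The strongest reply is that 9.3.7 is ambiguous rather than a firm deletion rule. A portion is undefined and could mean the affected visit or condition. The clause in 9.3.1 on withdrawn participants has little purpose if anyone leaving before visit 2 is deleted anyway. This stands as a limit on the claim, which is why the claim concerns the most natural reading. It does not remove the need to act, because two defensible readings give different primary datasets.

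Second, the plan budgets for drop-out. Two deletions from 22 leave the planned 20, and calibration A then gives exactly 80.0%. This also stands: at the plan's own allowance the cost is about 4% in standard error and about 3 power points. Four of 22 is 18%, nearly twice the 10% allowance, and no passage describes loss of single runs. Those counts are illustrations.

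Third, the ratio of 3 rests on a two-beamformer model with effects as differences, whereas the reference study tested several beamformers, always with the talker in front. The coding assumption is supported by the reported figures: with −1/+1 coding, the setup and interaction SEs would be equal, but they are 0.2 and 0.4, as half-unit sum coding predicts. The other assumptions cannot be checked, so the any-ratio ranges are the safer figures.

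Fourth, 9.3.1 asks for participants with primary and secondary outcome data. Read strictly, that could exclude partial completers whatever 9.3.7 says. This is fair, and the fix has to cover it.

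**Conclusion.** The concern holds as a cheap improvement, with medium confidence. On its most natural reading, 9.3.7 discards participants who carry about 88% (visit 1 only) or 98% (one SRT missing) of a complete participant's information on the primary effect, at the variance ratio implied by the reference standard errors. The resulting loss of precision is modest with two incomplete participants and roughly doubles with four. The number of incomplete participants is assumed throughout.

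Power need not fall below 80%; under calibration B it stays above that level even with four deletions. No bias is claimed. A missed visit 2 still leaves a balanced 2 by 2, and for single missing SRTs the documents give no reason for the loss, so bias was not assessed. If nothing is missing, nothing changes.

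**What to change.** Add to 9.3.7: *Outcomes analysed by linear mixed models use all available measurements of every eligible participant (valid under missing at random); a complete-case analysis is a sensitivity analysis.* The subject-level rule can stay for the paired tests.

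Add one sentence to 9.3.1 stating that the analysis set is defined separately for each part, consistent with the timing in 9.3.4. The same sentence should make clear that having outcome data does not mean having every measurement; otherwise a strict reading of 9.3.1 would undo the change.

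The cost is two sentences and one extra sensitivity run. The planned model already accepts incomplete participants, so no new data, visits or participants are needed. The downside is explicit reliance on missing at random, which the complete-case run helps the reader to judge.

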11.1 Data Handling and record keeping/ archiving

All data and documents recorded during the clinical investigation are only accessible to the clinical investigation team and to the monitor. The contact data from the investigational site are never used in the clinical data management system (CDMS). Source data of clinical investigation and the source documents inclusive all notes get encoded. The code list for the participant identification is safely kept within the clinical investigation team and will be deleted 3 months after the end of the clinical investigation. Investigators will preserve confidentiality of all patients taking part in the study, in accordance with ISO14155 (GCP rules) and local regulations.

All computer and software used for data collection provide a login and restricted access at different stages: any computer used on the investigational and sponsor sites is password protected and need a personal login, the access to the CDMS is also restricted to the investigator and the monitor with a password. The collected data are then exported on a server with password protected access, for the statistician.

The CDMS system IBM Clinical Development is a unified, cloud-based system that offers all the electronic data capture and study coordination capabilities needed. Each clinical investigation team member and the monitor owns an account. In this clinical investigation, the IBM Clinical Development will be used as data management system (electronic database). Clinical investigation documents will be safely stored. Only team members will have access to the data.

The anonymized data will be retained for 10 years. The study-related coding list will be deleted from the data directory and the associated backups within three months after completion of the study Case Report Forms (CRF).

Clinical investigation data will be recorded both with paper Case Report Form (pCRF) and electronic Case Report Form (eCRF). For each enrolled participant, a CRF will be maintained. All CRFs will be kept current to reflect the participant's status at each phase during the course of this clinical investigation.

Participants cannot be identified in the CRF by name or initials and birth date but an appropriate coded identification (participant ID) is used. All clinical investigation team members are authorized for the CRF entries. If pCRFs will be used, the investigator's acronym as well as the participant ID will be filled in and data are entered into an electronic file for analysis by the respective investigator. Data will be monitored by the assigned monitor.

In case of correction or changes in the CRF, the investigator undertakes the correction by crossing out the word/sentence with a single horizontal line and by adding the correction including their personal identifier, the date and the justification.

11.2 Procedures to maintain and protect participant privacy.

The Sponsor and Principal investigator affirm and uphold the principle of the participant's right to privacy and that they shall comply with applicable privacy laws. Especially, anonymity of the participants shall be guaranteed when presenting the data at scientific meetings or publishing them in scientific journals.

Individual participant medical information obtained as a result of this clinical investigation is considered confidential and disclosure to third parties is prohibited. Participant confidentiality will be further ensured by utilizing participant identification code numbers to correspond to treatment data in the computer files. For data verification purposes, authorized representatives of the Sponsor, the monitor, CA or a EC may require direct access to parts of the data records relevant to the investigation team. The investigator should provide adequate time and facilities for monitoring visits.

Actions taken to guarantee participant privacy:

- Participant names and details, accessible for monitor, appropriate investigators and Principle Investigator are documented in the Participant Identification log. There is no disclosure of personal information to no one else but the investigation team.
- Participant paper based files will be safely stored. Only members of the investigation team have access to these documents.
- Electronical data is uploaded in project files in CDMS and on SharePoint and just permitted to access by monitor, principal investigator and investigators.
- Source data is encoded and will be archived encoded as well. None of the participant names will be revealed to anyone than the clinical investigation team. Participants and their respective data will be tracked on source data and source documents via their participant

12 Amendments to the CIP

Substantial amendments are only implemented after approval by the EC. The use of waivers from the CIP is prohibited (Annex XV, Chapter 2, Art. 3.10 MDR).

13 Deviations from clinical investigation plan

Deviations from the CIP to protect the rights, safety and well-being of human participants under emergency circumstances may proceed without prior approval of the sponsor and the EC – such deviations will be documented and reported to the sponsor representative (Study Manager) and the EC as soon as possible. Apart from that the investigator is not allowed to deviate from this CIP unless that deviation does not influence the investigation data.

14 Device accountability

The accountability for investigational device will align to the procedures in Chapter 7.9 of ISO_14155, 2020. A device accountability log will be used to track the distribution of the investigational devices during the clinical investigation. In addition, information whether a device deficiency has occurred during the clinical investigation or not will be kept on the device accountability log.

15 Informed consent process

